### Reporting procedure for all SAEs

All SAEs need to be reported to the sponsor/legal representative and GSTT **within one working day** of the investigator team becoming aware of them.

Reports of related and unexpected SAEs should be submitted to ethics within 15 days of the Chief Investigator becoming aware of the event, using the SAE report form for non-CTIMPs published on the NRES website.

All reporting to GSTT R&D should be by [contact]) giving as much information about the incident as possible, and should be signed by the PI or Co-investigator. The GSTFT SAE reporting form should be used for GSTT sponsored studies.

The GSTT R&D Department will undertake an initial review of the information and ensure it is reviewed by GSTT R&D. Events will be followed up until resolution, any appropriate further information will be sent by the research team in a timely manner.

Reporting to the MHRA will be done in liaison with the Chief Investigator.

### **Risks and discomforts**

*Placement of electrodes:* In order for electrodes to be placed correctly the participant may be required to shave their chest. This may be uncomfortable. The adhesive electrode pads and the cream used to clean the skin before monitoring may cause minor irritation.

*Sniff manoeuvre:* Participants will be asked to perform a number of sniff manoeuvres with a nasal cannula. Participants may find this to be uncomfortable, but the procedures are safe. If participants start to feel lightheaded or short of breath they may begin to breathe normally.

*Skin irritation:* There may be a risk of skin irritation as a result of prolonged use of the physical activity monitor.

## **11.1 Ethics Reporting**

The study will be performed in line with the declaration of Helsinki and local procedures including approval by the research ethics committee.

Whilst it is not expected that the trial measurements will be related to any SAE, patients hospitalised due to exacerbations of COPD have high rates of both rehospitalisation and death within 30 days of discharge.

## **11.2 Trial Steering Committee**

This is an observational study, which has minimal risk to the study subjects. A Data Monitoring Committee (DMC) will not be utilized in this study. Site monitoring and oversight will be provided by the local R&D departments in line with local and national regulations on trial conduct.

The study will be conducted in accordance with the current approved protocol, ICH GCP, relevant regulations and standard operating procedures.

## **11.3 Ethics & Regulatory Approvals**

This study will be submitted for NHS ethical review.

## **12 Compliance and withdrawal**

### **12.1 Subject compliance**

Patients will undergo inpatient monitoring by an investigator who will also perform home assessments. Patients will also complete a daily symptom diary which will be reviewed at each assessment.

### **12.2 Withdrawal / dropout of subjects**

Each participant has the right to withdraw from the study at any time. In addition, the investigator may discontinue a participant from the study at any time if the investigator considers it necessary for any reason including:

- Ineligibility (either arising during the study or retrospective having been overlooked at screening)

- Disease progression which requires discontinuation of the study medication or results in inability to continue to comply with study procedures
- Consent withdrawn
- Lost to follow up

The reason for withdrawal will be recorded in the CRF.

## **12.3 Protocol Compliance**

No protocol compliance issues are anticipated. Any compliance issues that arise will be reported to the study sponsor.

# **13 Data**

## **13.1 Data to be collected**

All data will be collected by the research team.

### *Baseline assessment*

Demographics (age, height, weight), co-morbidities, pack year history, medication (acute and chronic), chest radiograph, blood tests (haemoglobin, white cell count, platelets, urea, creatinine, CRP, venous blood gas), arterial blood gas and observations (heart rate, blood pressure, respiratory rate, oxygen saturations and supplementary oxygen flow rate) will be obtained from the electronic patient medical record system.

EXACT-PRO and COPD Assessment Tool (standardised questionnaires) will be completed by the participant.

Pre-morbid data on participants' exacerbation frequency, lung function tests and eMRCD score will be collected from conversation with the patient and medical records.

The investigator will measure participants' spirometry (FEV1, FVC, IC) and NRD and clinical examination for signs of right and/or left ventricular failure.

### *Hospital assessments*

Measurements of heart rate, blood pressure, respiratory rate, oxygen saturations and supplementary oxygen flow rate and NRD will be collected by the investigator. Participants will complete the EXACT-PRO questionnaire daily.

### *Pre-discharge measurements*

On the day of discharge, medical records will be used to collect data on acute and chronic medications, most recent blood tests (haemoglobin, white cell count, platelets, urea, creatinine, CRP) and most recent arterial blood gas analysis.

Heart rate, blood pressure, respiratory rate, oxygen saturations and supplementary oxygen flow rate, spirometry (FEV1, FVC, IC) and NRD will be measured by an investigator. Participants will complete the EXACT-PRO and CAT questionnaires. Patients will be issued with wrist-worn watch-like physical activity monitors which will be collected at the end of the study. These physical activity monitors measure activity by recording and analysing readings from the on-board accelerometer and are designed to be comfortable so they can be worn safely 24 hours a day and have battery lives exceeding 6 months. No patient information is contained in the monitors or in the encrypted data files. De-identified physical activity data will be downloaded which will be collected and analysed at the end of the study.

### *Hospital discharge and subsequent readings*

Participants will receive home visits by an investigator who will perform NRD measurement, help the participant to complete the EXACT-PRO questionnaire and review participants' symptom diary. The CAT questionnaire and spirometry (FEV1, FVC, IC) will be measured weekly.

The final study visit at day 30 will ensure completion of questionnaires and collection of physical activity monitors.

### **13.2 Data handling and record keeping**

All documents will be stored safely in confidential conditions on the Lane Fox Unit, St Thomas' Hospital. On all study-specific documents, other than the signed consent, the participant will be referred to by the study participant number/code, not by name.

Personal data will be stored for 6-12 months after the study has ended. Research data generated by the study will be stored for 5 years.

Data will be handled in accordance with the Data Protection Act 1998.

[name] is responsible for data collection, recording and quality.

## **14 Statistical considerations**

### **14.1 Sample size calculation (some pilot/feasibility studies may not require a formal sample size calculation)**

A sample size of 30 has been set. This study is a pilot feasibility study with no prior data to power the sample size. As such, the sample size was not determined based on power analysis but will provide sufficient data to inform a larger future study. Data collected during this study will be used for sample size calculation for validation of future work. Recruitment will continue until 30 patients have completed the study.

### **14.2 Statistical analysis**

For all analyses,  $p<0.05$  will be deemed statistically significant. Comparison of data with one or more factors will be analysed using independent or paired t-test and ANOVA with repeated measures (if needed) for normally distributed data, and non-parametric tests in cases of non-normally distributed data, whenever applicable. Measures of association between the defined indices of NRD, the monitored endpoints and routinely used metrics will be investigated (e.g. using regression analysis). At last, univariate and multi-variate logistic regression may be employed to evaluate the predictive value of a number of investigated features (using the Receiver Operating Characteristic Methodology).

Interim analysis will be performed after 5 patients have been readmitted.

[name] (King's College London) will be involved in statistical analysis for the study. The Lane Fox Research Unit has an existing contract with [name] for *ad hoc* statistical support.

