- The majority of the 10 patients (7/10) could perform self-measurements with acceptable reproducibility and accuracy, as assessed by inter-occasion reliability and inter-observer reliability (note that in that study the coordinator also performed a measurement every day, which allowed to compare measurements between the coordinator and each patient). Some

promising directions for improvement were also identified at different levels (algorithm, form factor, user experience and instructions for use).

Overall, further data (larger sample size and higher COPD severity) are required to validate the level of reproducibility of the NRD measurement, also in conjunction with the ability to detect clinically relevant change in NRD due to deterioration in the home.

This study will be a single arm, pilot feasibility prospective observational study to assess whether NRD when utilized as an objective monitoring signal, is able to detect a clinical respiratory deterioration (re-exacerbations or failure to respond to treatment) in COPD patients within 30 days of discharge from hospital, following index hospitalization for AECOPD. The goal of using this advanced physiological biomarker is to facilitate early intervention and prevent hospital readmission and/or reduce the impact of relapse. As a pilot feasibility study, the aims are to assess the practical limitations to acquiring NRD in the home setting. Furthermore, data will be collected to assess the potential for NRD to detect and predict re-exacerbations allowing potential sensitivity and specificity to be calculated. If this pilot study confirms that NRD measurements are practical to acquire at home and successfully detect and predict future exacerbations of COPD, this will facilitate a study to validate the use of the Myotrace device by patients themselves in detecting and predicting AECOPD at home following index hospitalization for AECOPD.

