## 7 Study design & Flowchart

### 7.1 Study Design

#### **Primary end-point:**

Change in NRD from baseline to day prior to an acute exacerbation of COPD.

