#### **Secondary end-points:**

Change in NRD from peak exacerbation (hospital) to recovery baseline (home)

Correlation of time to recovery as measured by NRD and EXACT-PRO

Correlation of NRD, EXACT-PRO and daytime activity from hospital discharge to recovery

Physician-assessed exacerbation within 30-day post-discharge

Self-treated exacerbation within 30-day post-discharge

All cause hospital readmission within 30-day post-discharge

Mortality within 30-day post-discharge

Recovery as defined by the EXACT-PRO within 30-day post-discharge

Medication change within 30-day post-discharge

Unplanned healthcare contacts

Attendance of emergency department (without admission)

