### 9.3 Schedule of assessments for each visit

#### Baseline assessments

Enrolled patients will have clinical review and the following data collected at the 1st study assessment:

- The following data will be obtained from electronic patient records:
  - Age, height, weight,
  - Pack year history
  - Comorbidities
  - Medications (acute & chronic)
  - Premorbid data (exacerbation frequency, spirometry (FEV1, FVC, IC), extended Medical Research Council Dyspnoea (eMRCD) score)
  - Chest radiograph
  - Admission venous blood results: Haemoglobin, white cell count (including differential), platelet count, urea, creatinine, C-reactive protein, venous blood gas
  - Arterial blood gas on admission
  - Vital observations (heart rate, blood pressure, respiratory rate, oxygen saturations and supplementary O2 flow rate) at the time of the investigator assessment
- The following data will be obtained by measurements taken by the investigator:
  - eMRCD Score
  - EXACT-PRO questionnaire
  - COPD assessment test (CAT)
  - Body composition (Fat Free Mass)
  - Clinical examination for signs of right and/or left ventricular failure
  - Spirometry – FEV1, FVC, IC
  - Neural respiratory drive (NRD) – resting and maximal manoeuvres to obtain RMS EMGpara (microvolts), RMS as percentage of maximum (EMGpara%max) and Neural Respiratory Drive Index (NRDI). The procedure for NRD measurement is described below.

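### Section 14.2 applies an unqualified p<0.05 significance rule to every analysis of a pilot that was not powered and names no primary NRD index

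*Protocol*

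**What the plan says.** - **Threshold.** Section 14.2 states that, for all analyses, p<0.05 "will be deemed statistically significant". It gives no exploratory label, no sidedness and no order of importance among the analyses.
- **Tests.** The same section plans t-tests and repeated-measures ANOVA, with "non-parametric tests in cases of non-normally distributed data" where applicable. It adds associations between the NRD indices, the endpoints and routine metrics, and possibly logistic regression with ROC methods. An interim analysis follows the fifth readmission.
- **Sample size.** Section 14.1: "A sample size of 30 has been set", and "the sample size was not determined based on power analysis". The data are to support the sample size calculation of later work.
- **Endpoints.** Section 7.1 lists one primary endpoint, "Change in NRD from baseline to day prior to an acute exacerbation of COPD", and 11 secondary endpoints, the last being "Attendance of emergency department (without admission".
- **Indices.** Section 9.3 (Baseline assessments) lists EMGpara in microvolts, then "RMS as percentage of maximum (EMG para%max ) and Neural Respiratory Drive Index (NRDI". None is named as primary.
- **Next step.** Section 5 opens its sentence on a follow-on validation study with "If this pilot study confirms that NRD measurements are practical to acquire at home and successfully detect and predict future exacerbations".

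**The concern.** A study that is not powered and is meant to inform the design of the next one needs estimates and their precision. Section 14.2 instead gives every analysis the same pass/fail label. That label can mislead in two ways.

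- **False positives.** Many unadjusted tests on related indices can produce a result called significant when NRD carries no information.
- **False negatives.** The primary endpoint has a value only in patients who re-exacerbate, so it may rest on a handful of pairs. A real pre-event rise in NRD could then be reported as not significant.

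An analysis plan that called the results descriptive would conflict with the protocol's own sentence, so the protocol text is the place to correct.

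**Working it through.** The plan has no power figure to reproduce, because section 14.1 says the size of 30 was not derived from one.

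**Inputs from the protocol:** 30 patients; threshold 0.05; 1 + 11 = 12 endpoints (section 7.1); 3 indices (section 9.3); 20% readmission within 28 days (section 11); 7.1% 30-day AECOPD readmission in the US data (section 5); interim at 5 readmitted patients (section 14.2).

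**Assumptions:** two-sided tests; Wilcoxon signed-rank as the paired non-parametric test; effect sizes in SDs of the within-patient change; correlation of 0.5 between test statistics. The protocol gives none of these.

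**1. Chance of at least one false positive if NRD is uninformative**

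Independent tests: 1 − 0.95^k. Correlated tests: simulation of equicorrelated normal statistics.

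| Tests (k) | Independent | Correlation 0.5 | Expected false positives (0.05 × k) |
|---|---|---|---|
| 3 (primary endpoint, three indices) | 14% | – | 0.15 |
| 12 (one per endpoint) | 46% | about 32% | 0.6 |
| 36 (12 × 3) | 84% | about 55% | 1.8 |

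The 36 is a ceiling for the endpoint-by-index grid, not a count that the protocol prescribes. The three indices are linked: section 9.3 (NRD measurement) derives EMGpara%max from EMGpara, and the respiratory-rate product from EMGpara%max. Positive correlation lowers the chance of any false positive, so 84% is an upper figure for 36 tests.

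**2. Power of the primary paired comparison**

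If events equal readmissions, the expected number of pairs is 30 × 0.20 = 6. Power comes from the noncentral t distribution with n − 1 degrees of freedom and noncentrality d√n, two-sided 5%.

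| Pairs | 0.5 SD | 0.8 SD | 1.0 SD | 1.5 SD |
|---|---|---|---|---|
| 6 | 17% | 36% | 51% | 83% |
| 9 (assumed) | 26% | 56% | 75% | 98% |
| 12 (assumed) | 35% | 71% | 88% | >99% |

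The rows for 9 and 12 are included because section 5 also counts physician-assessed and self-treated exacerbations, for which the protocol gives no rate. At 6 pairs the 95% confidence interval for the mean change has half-width 2.571/√6 = 1.05 SD.

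**3. Smallest attainable signed-rank p-value**

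The two-sided exact minimum is 2/2^n: 0.125 at n = 4, 0.0625 at n = 5 and 0.031 at n = 6. With 5 pairs or fewer the test cannot reach 0.05 even if every patient changes in the same direction. At n = 5 a one-sided exact test could reach 0.031. A two-sided normal approximation could reach 0.043 without continuity correction and 0.059 with it.

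**4. Chance of 5 or fewer events among 30 (binomial)**

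- 98% at 7.1%
- 43% at 20%
- 8% at an assumed 30%

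The first two rates are for readmission, so they understate the number of exacerbations as the protocol defines them.

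**The case against.** The strongest reply is that a conventional 0.05 statement does not make a study confirmatory. The protocol calls itself a pilot feasibility study throughout and discloses that it was not powered. Multiplicity handling and confidence intervals commonly sit in an analysis plan, which is not shown here.

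Much of the detail in this reply stands:

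- Eight of the 12 endpoints are single-arm outcomes, such as readmission, mortality and medication change. They produce a test only if they are related to NRD, and section 14.2 does not require every index to be tested against every endpoint.
- The 20% is a readmission rate, not an exacerbation rate.
- The power figures depend on assumed effects. At 1.5 SD, 6 pairs already give 83%.

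Three stronger readings are tempting and are not supported:

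- **The rank test can never succeed.** At the expected 6 pairs its two-sided exact minimum is 0.031. The limit applies at 5 pairs or fewer, for a two-sided exact test, and the protocol fixes neither the test nor its sidedness.
- **The follow-on decision rests on a p-value.** No section says so. The sentence in section 5 is introductory and names no test, and the text just before it speaks of calculating sensitivity and specificity.
- **Significance must never be declared.** That is a reporting preference, not the correction of an error.

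The reply does not remove the rule itself. Section 14.2 fixes the significance label for all analyses without qualification, so this is more than detail left for later.

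**Conclusion.** The point holds as a badly fixed rule: an unqualified significance label for every analysis does not fit a study that section 14.1 describes as unpowered and as a source of planning data.

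The false-positive risk is material. It runs from 14% (the primary endpoint on three independent indices) to an upper figure of 84% (36 independent tests), with about 32% for 12 tests and 55% for 36 at correlation 0.5. Where it falls depends on how many tests are run and how strongly they are correlated.

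The primary comparison is weak for changes up to about 1 SD if only 6 patients have an event, and better if non-admitted exacerbations add pairs. The signed-rank limit is conditional. It would apply at the interim analysis if that used only the 5 readmitted patients and a two-sided exact test.

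The change is worth making because it alters what the study can claim, while data collection and recruitment stay as they are.

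**What to change.** In section 14.2, replace the significance sentence with: *All analyses are exploratory; estimates are reported with 95% confidence intervals, and p-values are descriptive and unadjusted for multiplicity.*

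For the primary endpoint, add that each patient's pre-event change will be reported, together with the mean or median and its confidence interval.

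The cost is about two sentences. The downside is that no confirmatory significance claim can be made from the pilot.

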#### **9.6 End of Study Definition**

The trial will cease when the final patient has completed 30 days of home monitoring or has an exacerbation requiring hospital re-admission or 12 months from trial initiation, whichever is sooner.

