AECOPD is a clinical diagnosis made when a patient with COPD experiences a sustained (e.g. 24–48 h) increase in cough, sputum production, and/or dyspnoea. It commonly occurs in the cohort of patients under investigation in this study, who are at high risk of developing an AECOPD and indeed 20% will be readmitted to hospital within 28 of being discharged (when the primary reason for admission was AECOPD). The Chief Investigator and Principal Investigator therefore deem AECOPD to be an expected AE and SAE and AECOPD will not be reported to the sponsor. In the event of a participant developing an AECOPD, this will be documented in the participant's medical notes and case record file.

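### If repeated-measures ANOVA were run on the full 30-day home NRD series, it would drop readmitted patients and anyone with a missed visit; a mixed model should be named instead

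*Protocol*

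**What the plan says.** Section 14.2 gives a general list of methods. Comparisons use "independent or paired t-test and ANOVA with repeated measures (if needed) for normally distributed data", and non-parametric tests where the data are not normal. Associations between NRD indices and other measures "will be investigated (e.g. using regression analysis", with no form of regression fixed. Logistic regression with ROC methods may also be used. No method is tied to a particular endpoint or set of days.

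The following sections bear on the shape of the data:

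- **Section 9.4:** home visits start the day after discharge and keep the same time of day; the last is at day 30.
- **Section 9.3:** hospital NRD is measured twice a day until discharge.
- **Section 9.6:** the trial closes when the last patient finishes 30 days at home or "has an exacerbation requiring hospital re-admission", or at 12 months if that is sooner.
- **Section 11:** of patients like these, "20% will be readmitted to hospital within 28 of being discharged" (the unit is missing; I read days).
- **Section 14.1:** "A sample size of 30 has been set", and "Recruitment will continue until 30 patients have completed the study".

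Section 6 makes the NRD trajectory and its relation to symptoms a secondary objective. Section 7.1 lists as a secondary endpoint the correlation of NRD, EXACT-PRO and activity between discharge and recovery. The primary endpoint in Section 7.1 is a difference between two readings, at baseline and on the day before an exacerbation.

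**The concern.** The only method in the list that is built for repeated readings assumes a complete, balanced series, and this design will not produce one. Hospital stays differ in length, home monitoring appears to end at readmission, and some visits will be missed or yield no usable signal. A complete-case analysis over the whole home window would therefore leave out the patients with the most severe relapses, in a study that asks whether NRD signals relapse. The loss would also be related to outcome. Section 14.1 intends the data to inform the sample size of later work, so a trajectory variance estimated without readmitted patients could carry forward.

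**Working it through.** The plan gives no figure to reproduce: 30 was chosen without a power calculation, and no complete-case number is stated. The check is how many patients a classical repeated-measures ANOVA over the full home window could use.

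**Inputs from the protocol**
- N = 30 (Section 14.1).
- Readmission r = 0.20 (Section 11), so 30 × 0.20 = 6 expected. The binomial chance of at least 5 is 0.74.

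**Assumptions**
- V = 30 home readings per patient. Home NRD is never called daily, but next-day visits at a fixed time and an endpoint that uses the day before an exacerbation imply it.
- A readmitted patient's home series stops at readmission.
- Per-visit missingness m is independent across visits. The protocol gives no rate, so a range is shown.

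**Complete series expected** = 30 × (1 − 0.20) × (1 − m)^30

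| m | (1 − m)^30 | Complete, of 30 |
|---|---|---|
| 0% | 1.000 | 24.0 |
| 1% | 0.740 | 17.8 |
| 2% | 0.545 | 13.1 |
| 5% | 0.215 | 5.2 |
| 10% | 0.042 | 1.0 |

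**When more than half are lost.** Solve 0.80 × (1 − m)^30 = 0.5, so (1 − m)^30 = 0.625 and m = 1 − 0.625^(1/30) = 1.55%. With no readmissions, m = 1 − 0.5^(1/30) = 2.28%.

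**Shorter windows.** If readmissions are spread evenly over 28 days, a window of k days keeps 6 × (28 − k)/28 readmitted patients: 4.5 of 6 at 7 days, 3.0 at 14 days, and none for the full 30 days.

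**What a model using all readings would keep.** Take a mean of 14 home days for readmitted patients. Observed patient-days are 900 × (1 − m) × (0.8 + 0.2 × 14/30), which is about 788 at m = 2% and 764 at m = 5%. The ANOVA would use 30 days from each complete patient, about 393 and 155.

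**Illustration.** One data set was simulated with 5% missing visits and 6 readmissions. Three of 30 patients were complete, none of them readmitted. A standard repeated-measures ANOVA routine rejected the data as unbalanced. A linear mixed model used all 30 patients and 777 readings.

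**The case against.** The strongest reply is that Section 14.2 never assigns this ANOVA to the home series. It is conditional, sits in a general list, and comes with no set of days and no complete-case rule. The trajectory objective asks how NRD relates to symptoms, which Section 14.2 could address through regression. The detailed model may be in an analysis plan that is not shown. All of this stands, and it limits the point to what would happen if the named method were used on the full series. It does not remove the point: the one repeated-measures method that the protocol does name is a poor fit, and the regression mentioned is an unspecified example that says nothing about within-patient correlation.

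A reader might infer three stronger things that the documents do not support:

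- **That most patients would be discarded.** This depends on a missingness rate that the protocol does not give. On its own figures the loss is about 20%. Nor can the 6 readmitted patients simply be subtracted from a complete-case count, because many would already be incomplete. At 5% missing, 30 × 0.215 = 6.4 falls to 5.2, a further loss of about 1.3.
- **That every relapser is excluded, so that only patients without relapse are described.** Section 5 also defines physician-assessed exacerbations without admission, and self-treated ones. Nothing in the protocol stops home visits for these patients.
- **That the protocol sets a stopping rule for every readmitted patient.** Section 9.6 is worded for the final patient. It suggests that home monitoring ends at readmission but does not say so for each patient.

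A loss-of-power argument carries little weight, since "the sample size was not determined based on power analysis". Section 14.1 also leaves open whether a readmitted patient counts as having completed, so the number enrolled may exceed 30.

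**Conclusion.** The point holds in conditional form, as a modest and cheap improvement to secondary analyses of a pilot study. Classical repeated-measures ANOVA or Friedman over the full 30-day home window would drop patients whose series ends at readmission, about 6 of 30, and would keep about 24 at most. Any further loss depends on visit completeness: at assumed losses of 1% to 10% per visit, about 17.8 down to 1.0 patients remain. These figures assume daily home readings, independent missed visits, a window running to day 30, and no home readings after readmission. The primary endpoint is not affected, because a readmitted patient can still contribute both the baseline and the day-before readings.

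**What to change.** In Section 14.2, for the secondary NRD trajectory analyses in Sections 6 and 7.1, replace repeated-measures ANOVA with a linear mixed model fitted to all available readings. Include a patient random intercept, and a random slope if it can be estimated. Take time as day from discharge, and include relapse status by time for the contrast between relapse and no relapse. Use time from onset only within relapsers, since it is undefined for everyone else.

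The cost is wording only: standard software fits the model and no new data are needed. There are two drawbacks. The model assumes that readings are missing at random given those observed, which may fail if a patient worsens after the last reading and is then admitted. With about 30 patients, a random slope may not be estimable.
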